4.2.3 Exploratory endpoints

4.2.3.1 Exploratory safety endpoints

- Number of adverse events related to technical complaints during at least 24 weeks from treatment onset
- Number of adverse events related to technical complaints during at least 76 weeks from treatment onset

Protocol
Trial ID:NN7415-4255
UTN:U1111-1179-3872
EudraCT no.:2016-000614-29

~~CONFIDENTIAL~~

Date:
Version:
Status:
Page:

28 December 2017
4.0
Final
28 of 124

Novo Nordisk

4.2.3.2 Exploratory patient-reported outcome endpoints

- Change in Hemo-TEM after 24 weeks from treatment onset
- Change in Hemo-TEM after 76 weeks from treatment onset
- Change in SF-36v2 after 24 weeks from treatment onset
- Change in SF-36v2 after 76 weeks from treatment onset
- Change in SDS after 24 weeks from treatment onset
- Change in SDS after 76 weeks from treatment onset
- Change in TSQM after 24 weeks from treatment onset
- Change in TSQM after 76 weeks from treatment onset
- Change in SIAQ-ISRQ after 24 weeks from treatment onset
- Change in SIAQ-ISRQ after 76 weeks from treatment onset
- Status of PGI-C after 24 weeks from treatment onset
- Change in H-DAT after 76 weeks from treatment onset

4.2.3.3 Exploratory pharmacokinetic and pharmacodynamic endpoints

- Concentration of concizumab over time during 24 hours PK assessment
- Concentration of free TFPI over time during 24 hours PD assessment
- Thrombin generation over time during 24 hours PD assessment
 - Peak of thrombin generation time during 24 hours PD assessment
 - ETP time during 24 hours PD assessment
 - Velocity index time during 24 hours PD assessment

All endpoints referring to a time frame of either 24 weeks or of at least 24 weeks will be evaluated in the main part of the trial.

All endpoints referring to a time frame of 76 weeks will be evaluated in the extension part of the trial.

Protocol
 Trial ID: NN7415-4255
 UTN: U1111-1179-3872
 EudraCT no.: 2016-000614-29

~~CONFIDENTIAL~~

Date:
 Version:
 Status:
 Page:

28 December 2017
 4.0
 Final
 29 of 124

Novo Nordisk

5 Trial design

5.1 Type of trial

The trial is a multicentre single-arm trial, which aim to evaluate the efficacy and safety of concizumab 0.15 mg/kg (with potential dose escalation to 0.20 and 0.25 mg/kg) administered daily s.c. in patients with severe haemophilia A without inhibitors. The selected dose regimen is based on relevant PK and TFPI data as well as PK/PD modelling from the preceding explorer™ trials. Both on-demand and prophylaxis patients will be eligible for the trial.

[figure not shown]

Figure 5–1 Schematic diagram of the trial design

The total trial duration for the individual patient will be approximately 86 weeks, including a 2-week screening period, a subsequent 76-week treatment period and an 8-week follow-up period, see [Figure 5–1](#).

The 76 weeks treatment period is further split into a main part which lasts at least 24 weeks for all patients in the trial and an extension part which lasts 52 weeks. After completion of the main part of the trial, patients will continue into the extension part. All available data up to the time point where the last patients ends 24 weeks of treatment (or have withdrawn) will be used in the analysis of the main part, see Section [17.7](#).

Breakthrough bleeding episodes occurring from visit 1 to end-of-trial visit will be treated by the patients at home with FVIII at the discretion of the investigator, who will also choose dose levels. Only turoctocog alfa/NovoEight® will be provided and paid by Novo Nordisk for this purpose.

The analysis of the main part (after 24 weeks) of the trial aims to substantiate CPoC that concizumab has the potential to prevent bleeding episodes in patients with severe haemophilia A without inhibitors. The extension part will provide additional safety data on 52 weeks dosing of concizumab.

Protocol
 Trial ID:NN7415-4255
 UTN:U1111-1179-3872
 EudraCT no.:2016-000614-29

~~CONFIDENTIAL~~

Date: 28 December 2017
 Version: 4.0
 Status: Final
 Page: 30 of 124

Novo Nordisk

Human biosamples (plasma, serum, and/or DNA for genotyping) will be collected in this trial for future exploratory analysis to pursue a deeper insight into the biology of TFPI, coagulation, and effect of concizumab on joint health that may include coagulation parameters and markers of joint status or damage. Acceptance of storage of human biological specimens is voluntary and will not affect the patients' participation in the trial. Therefore, patients will have the possibility to sign the informed consent for the trial and participate, while refusing permission for biological specimens to be stored for future exploratory analysis. Please refer to Section [24.1](#) for further information.

An independent data monitoring committee (DMC) will be established for this trial. The DMC will review all safety data from all ongoing trials with concizumab exposure, see Section [12.8.2](#).

All patients will be asked to perform a 24 hour PK-session after treatment with concizumab is initiated.

5.1.1 Surgery

Minor surgery is allowed in this trial. Major surgery conducted more than one month (30 days) prior to trial start is allowed, see exclusion criterion no 6.

Minor surgery is defined as an invasive operative procedure where only the skin, the mucous membranes or superficial connective tissue is manipulated. Examples of minor surgery include implanting of central venous access devices (ports, CVC, pumps and other CVADs) in subcutaneous tissue, skin biopsies or simple dental procedures.

5.2 Rationale for trial design

ExplorerTM5 is a phase 2, clinical proof of concept (CPoC) and safety trial. The trial aims to substantiate CPoC that concizumab has the potential to prevent bleeding episodes in haemophilia patients without inhibitors. A dose escalation design will allow cautious dose escalation in order to choose the efficacious and safe concizumab dose for the individual patient from the selected dose regimen Concizumab 0.15 mg/kg (with two potential dose-escalation steps, 0.20 mg/kg and 0.25 mg/kg) given s.c. once daily will be investigated.

The duration of 24 weeks for the main part of the trial is deemed necessary in order to obtain information on the annual bleeding rate (ABR) during concizumab prophylaxis. The duration of the extension part of the trial will be 52 weeks and will provide further information on long-term efficacy, i.e. ABR, and also provide additional safety data upon 76 weeks treatment with concizumab.

A total of 33 patients are planned to receive concizumab s.c. once daily in this single arm trial, please see [Figure 5-1](#).

The concizumab dose regimens will be starting with 0.15 mg/kg with the possibility to escalate to 0.20 mg/kg and 0.25 mg/kg, see section [5.3.1](#).

Protocol
 Trial ID: NN7415-4255
 UTN: U1111-1179-3872
 EudraCT no.: 2016-000614-29

~~CONFIDENTIAL~~

Date:	28 December 2017	Novo Nordisk
Version:	4.0	
Status:	Final	
Page:	31 of 124	

Daily dosing with 0.15 mg/kg aims to ensure steady-state levels of concizumab plasma concentrations above 100 ng/mL for the majority of the patients starting on this dose. The PK results from explorerTM3 showed exposure-response in terms of fewer bleeding episodes recorded for patients who reached plasma concentrations of concizumab above 100 ng/mL see [Figure 3-1](#). The minority of patients which are predicted to have steady-state plasma concentrations below this threshold are expected to experience bleeding episodes and therefore will have the opportunity to be dose-escalated to the dose of 0.2 mg/kg. A further dose escalation to 0.25 mg/kg per day is permitted, again based on the bleeding rate, see section [5.3.1](#).

Figure 5-2 Individual predicted concizumab concentration profiles for all concizumab-treated patients in explorerTM2 (n=4 patients) and explorerTM3 (n=18 patients). The horizontal lines indicate 100 ng/mL, and the shaded areas represent the full range (min-max) of the individual predicted profiles¹.

¹ Plasma concentrations in the same range as those in explorerTM3 are expected to be reached in this trial with daily dose administration. The starting dose for all patients will be 0.15 mg/kg daily. The plasma steady-state exposure for a typical subject at this dose level is predicted to be fourfold lower compared to a typical subject on 0.8 mg/kg Q4D (cohort 3 of explorer³) in terms of both C_{max} and AUC 0-24h. For 0.20 mg/kg daily and 0.25 mg/kg, the plasma steady-state exposure levels for a typical subject are predicted to be less than 40% and 70% respectively, compared to the typical subject exposure in the 3rd cohort of explorerTM3 (AUC and C_{max}). The maximum predicted plasma exposure levels (C_{max} and AUC 0-24h) for the 0.15 mg/kg daily dose level is predicted to be more than 8 fold lower than for 0.80 mg/kg Q4D. For 0.20 mg/kg daily both C_{max} and AUC 0-24h are predicted to be more

Protocol
Trial ID: NN7415-4255
UTN: U1111-1179-3872
EudraCT no.: 2016-000614-29

~~CONFIDENTIAL~~

Date:	28 December 2017	Novo Nordisk
Version:	4.0	
Status:	Final	
Page:	32 of 124	

Due to the high between-patient variability in concizumab concentration observed in explorer^{TM3}, a significant overlap in plasma concentrations of concizumab in patients who received 0.25, 0.5 and 0.8 mg/kg doses was seen, see [Figure 5-2](#). Therefore, choosing three doses that would lead to reasonably distinct mean plasma concentrations of concizumab, and thus different efficacy at each dose level was not deemed possible. For this reason, a traditional parallel arm design was not chosen for the phase 2 trials. In contrast, the titration trial design allows patients to start on a low dose, which is expected to ensure prophylaxis but not marked changes in coagulation parameters, for the majority of patients. Escalation to the next dose level will only occur in the case of lack of efficacy (≥ 3 spontaneous bleeding episodes within the preceding 12 weeks). In addition, the PK of concizumab is heavily influenced by target mediated drug disposition, which means that small differences in concizumab dose ultimately leads to large differences in plasma concentrations. Therefore, daily dosing is proposed for the phase 2 trial, explorer^{TM5}. Daily dosing will allow for the increase in trough levels and thus better efficacy may be expected with a lower dose.

Embryonic exposure in pregnant female partners of men treated with concizumab is highly unlikely and there is no need for protocol requirements for use of contraception in phase 2 and 3 trials.

than 3 times lower than for 0.80 mg/kg Q4D. For 0.25 mg/kg daily, the maximum C_{max} and AUC 0-24h are predicted to be 35 % lower than for 0.80 mg/kg Q4D.

Protocol
 Trial ID: NN7415-4255
 UTN: U1111-1179-3872
 EudraCT no.: 2016-000614-29

~~CONFIDENTIAL~~

Date: 28 December 2017
 Version: 4.0
 Status: Final
 Page: 33 of 124
Novo Nordisk

5.3 Treatment of patients

Table 5–1 List of products provided by Novo Nordisk

Compound Name	Strength	Dosage form	Route of administration	Treatment period
Concizumab B²,	100 mg/mL	3 mL solution in a 3 mL cartridge ³ .	S.c. administration using NovoPen [®] 4	For prophylactic treatment for 76 weeks.
Turoctocog alfa (NovoEight[®])⁴, Sodium chloride solution 4ml	2000 IU/vial	Powder for solution for injection Solvent for solution for i.v. injection used for reconstitution of turoctocog alfa.	I.v. administration	For treatment of breakthrough bleeding episodes (or prophylaxis in the screening and follow-up phases), at the discretion of the treating physician (patients may choose to use other familiar pre-trial FVIII drug). For further information see section 5.3.2

Concizumab will be given s.c., once daily for a total dosing period of 76 weeks.

The NovoPen[®]4 injector will be supplied by Novo Nordisk and used for the s.c. administration of concizumab. It will be labelled in accordance with national legislation and a copy of the label can be found within the Trial Materials Manual, see Section [9.1](#).

The first dose of concizumab will be given at the trial site under medical supervision. After the initial dose the patient must be observed for potential emergence of AEs/safety signals for at least 2 hours at the trial site. At the screening visit and the first scheduled treatment visit patients will be trained in s.c. administration of concizumab with NovoPen[®] 4 and in the use of eDiary.

Investigational medicinal product (IMP)

³ Not to be confused with the daily injected volume (~150 µL, depending on dose strength and body weight)

⁴ Non-investigational medicinal product (NIMP)

Protocol
 Trial ID: NN7415-4255
 UTN: U1111-1179-3872
 EudraCT no.: 2016-000614-29

~~CONFIDENTIAL~~

Date:	28 December 2017	Novo Nordisk
Version:	4.0	
Status:	Final	
Page:	34 of 124	

In case safety concerns meet the criteria (See section [12](#)) for putting enrolment of additional patients on hold, further enrolment in the trial will be halted. Dosing of patients on treatment may continue while further evaluation is made by the safety committee. In case of other safety concerns all available data will be evaluated by the DMC see Section [12.8.2](#).

5.3.1 Dose escalation

Bleeding episodes will be assessed during the trial both at scheduled visits and also between visits. The first 2 weeks of the treatment with concizumab 0.15 mg/kg is considered as a run-in period. Hence the bleeding episodes occurring during the first 2 weeks should not influence a dose escalation decision.

All spontaneous bleeding episodes (sBEs) are counted from 2 weeks after visit 2 (first-dose visit) until visit 16 (end-of-treatment visit), i.e. a total of 74 weeks. Dose-escalation will be based on the number of spontaneous, treated bleeding episodes in patients within preceding 12 weeks. However, before dose-escalation can occur, to ensure the safety of the patients, the investigator must take into account the full clinical picture the patient is presenting with and all available laboratory results, including coagulation parameters.

Dose 0.15 mg/kg:

When a sBE occurs, the investigator will determine if ≥ 3 sBEs have occurred within the preceding 12 weeks since visit 2+2weeks (including the current sBE). If yes, and if investigator deems it safe, the patient will have to be dose escalated from 0.15 to 0.20 mg/kg at the next scheduled visit. If the investigator judges that this visit is scheduled too late, he/she should contact the patient for an unscheduled visit.

Dose 0.20 mg/kg:

When an sBE occurs, the investigator will determine if ≥ 3 sBEs have occurred within the preceding 12 weeks (including the current sBE), counting only new sBEs from the beginning of the 0.20 mg/kg treatment period. If yes, and if investigator deems it safe, the patient will have to be dose escalated from 0.20 to 0.25 mg/kg at the next scheduled visit. If the investigator judges that this visit is scheduled too late, he/she should contact the patient for an unscheduled visit.

Dose 0.25 mg/kg:

Patients are not dose escalated further regardless of the number of sBEs. When an sBE occurs, the investigator will determine if ≥ 3 sBEs have occurred within the preceding 12 weeks (including the current sBE), counting only the new sBEs from the beginning of the 0,25mg/kg treatment period. If yes, then the patient must be discontinued from treatment due to lack of efficacy, see Section [6.4](#).

Since the patient may have to wait up to 8 weeks for the next scheduled visit (in the extension part), the possibility of dose escalation at unscheduled visits is necessary for the dose-escalation eliciting bleeding episode to occur soon after previous scheduled visit.

Protocol
 Trial ID: NN7415-4255
 UTN: U1111-1179-3872
 EudraCT no.: 2016-000614-29

CONFIDENTIAL

Date:
 Version:
 Status:
 Page:

28 December 2017 | **Novo Nordisk**
 4.0
 Final
 35 of 124

[figure not shown]

Figure 5–3 Dose escalation of concizumab for one individual patient

5.3.2 Treatment of bleeding episodes during the trial

Bleeding episodes (main part, extension part, and follow-up part) :

Breakthrough bleeding episodes during the course of the trial will be treated at the discretion of the treating physician, with either turoctocog alfa/Novoeight[®] (rFVIII) (provided by Novo Nordisk) or other non-modified FVIII products (not provided by Novo Nordisk) . Treatment dose is chosen at the discretion of the investigator; however; in this trial any given single dose should not exceed 50 IU/kg (Table 8-4). The patient can treat himself and then he must call the site. The bleeding episodes must be recorded in the eDiary. Bleeding episodes must be recorded in the electronic case report form (eCRF) as an AE/SAE if fatal, life threatening or evaluated as related to trial product (see section 12.1)

FVIII prophylactic treatment (follow-up part) :

During the follow-up part of the trial (i.e. from concizumab end-of-treatment visit to end-of-trial visit) patients will receive pre -trial FVIII medication at the discretion of the treating investigator, who will also choose dose levels. Only turoctocog alfa/NovoEight[®] will be provided by Novo Nordisk for this purpose.

5.3.3 Prohibited medication

- Treatment with anti-fibrinolytics (e.g. tranexamic acid, aminocaproic acid)*
- Heparin, except for sealing of central venous access ports according to local practice
- Vitamin-K antagonists
- Direct oral anti-coagulants (DOACs)

Protocol
 Trial ID:NN7415-4255
 UTN:U1111-1179-3872
 EudraCT no.:2016-000614-29

~~CONFIDENTIAL~~

Date: 28 December 2017
 Version: 4.0
 Status: Final
 Page: 36 of 124

Novo Nordisk

- Modified FVIII products with extended half-life

*Local/topical use is allowed. Use of single systemic doses in severe bleeding episodes, after careful benefit-risk evaluation, is allowed.

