5.5 Rationale for treatment

Concizumab is a monoclonal antibody and as such offers the possibility of s.c. administration. S.c. administration of an effective prophylactic drug has potential to reduce treatment burden significantly compared to the currently approved prophylactic drugs which have to be administered i.v.

The treatment period of 24 weeks (the main part of the trial) is considered necessary for providing data that allow demonstration of CPoC and to support decision-making regarding a phase 3 confirmatory trial. Dosing for an additional 52 weeks will provide valuable long-term efficacy and safety.

Breakthrough bleeding episodes may occur during prophylactic regimens with conventional FVIII replacement therapy. Therefore, it is expected that breakthrough bleeding episodes will also occur during prophylaxis with concizumab even if clinical proof of concept is demonstrated. Consequently turoctocog alfa (FVIII) will be provided by Novo Nordisk A/S in this trial for treatment of breakthrough bleeding episodes.

Patients are not obliged to use turoctocog alfa (FVIII) and can use their previously used FVIII concentrate for treatment of breakthrough bleeding episode. Novo Nordisk A/S will not provide or reimburse these products.

Please refer to the Investigator's Brochure for further information.

Protocol
Trial ID:NN7415-4255
UTN:U1111-1179-3872
EudraCT no.:2016-000614-29

~~CONFIDENTIAL~~

Date: 28 December 2017
Version: 4.0
Status: Final
Page: 37 of 124

Novo Nordisk

6 Trial population

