8.1.7 Visit 1 (Screening part)

Informed consent must be obtained before any trial related activity, see Section [18.2](#).

In cases where a patient's baseline FVIII level is not documented in medical records, sampling for FVIII activity at screening should be postponed if the patient has received FVIII within 96 hours. Screening can take place between 14 to 21 days prior to planned enrolment day (visit 2). For prophylactic treatment (prior to Screening) with extended half-life FVIII products, this period should be extended to a time-period equal to 8 half-lives of the used product

All assessments to be performed at screening are listed in [Table 2-1](#), see Section [2](#).

Apart from informed consent patients will be asked to complete the ePRO questionnaires before any other trial related activities are performed according to Section [8.6](#);

- Hemo-TEM,
- VERITAS-Pro[®] or VERITAS-PRN[®]

Assessment results from physical examination, body measurements, as well as measurements of vital signs, urinalysis electrocardiogram (ECG) and details of any contemporary adverse events must be entered into the eCRF.

A screening confirmation call must be performed in the IWRS, at the day of the visit.

The investigator must review all information obtained from the screening procedures. If a patient does not meet all inclusion criteria or meets one or more of the exclusion criteria for the trial the patient does not qualify to be enrolled.

Patients will be provided with turoctocog alfa (rFVIII) trial injection kits and directions for use (DFU) to cover the potential FVIII treatment in the screening part of the trial and investigator will ensure that the patients are capable of treating themselves with rFVIII (turoctocog alfa). Patients on any previous FVIII prophylaxis can continue with this treatment until 48 hours before visit 2.

Dispensing of rFVIII (turoctocog alfa) should be performed in the IWRS

For bleeding episodes that occur in the period from Screening visit (Visit1) to enrolment visit (Visit 2) information about the bleeding episode is to be entered in the eCRF at visit 2.

Protocol
 Trial ID:NN7415-4255
 UTN:U1111-1179-3872
 EudraCT no.:2016-000614-29

~~CONFIDENTIAL~~

Date:	28 December 2017	Novo Nordisk
Version:	4.0	
Status:	Final	
Page:	45 of 124	

The patient should be instructed to call the site if any bleeding episodes, questions or issues arise after he has left the site.

8.1.8 Training of patients visit 1 and visit 2

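### For breakthrough bleeds on concizumab, section 5.5 and Table 5-1 permit the patient's own FVIII without limit, while 5.3.2 and 5.3.3 exclude extended half-life FVIII, whose users can enrol

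*Protocol*

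**What the plan says.** All references are to protocol version 4.0; version 3 reads the same on these points.

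- **Prohibition.** Section 5.3.3 includes "Modified FVIII products with extended half-life" in its list. It names no trial period, and the starred exception in that section belongs to the anti-fibrinolytics item only.
- **Eligibility.** Section 5.1 states: "Both on-demand and prophylaxis patients will be eligible for the trial". No criterion in 6.2 or 6.3 refers to the type of FVIII used. Section 8.1.7 gives a timing rule for users of extended half-life products: "For prophylactic treatment (prior to Screening) with extended half-life FVIII products, this period should be extended to a time-period equal to 8 half-lives".
- **Bleeds, restrictive text.** The first paragraph of 5.3.2 covers the main, extension and follow-up parts. It allows turoctocog alfa or "other non-modified FVIII products (not provided by Novo Nordisk").
- **Bleeds, permissive text.** Section 5.5 says: "Patients are not obliged to use turoctocog alfa (FVIII) and can use their previously used FVIII concentrate for treatment of breakthrough bleeding episode". Table 5-1 says "patients may choose to use other familiar pre-trial FVIII drug", and the same cell then refers the reader to 5.3.2.
- **Screening.** Section 8.1.7 lets a patient stay on whatever FVIII prophylaxis he was taking, up to 48 hours ahead of visit 2.
- **Follow-up.** The second paragraph of 5.3.2 says "patients will receive pre -trial FVIII medication at the discretion of the treating investigator". Section 5.4 separately provides for a switch to a suitable marketed product when trial product is stopped, at the investigator's discretion.

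**The concern.** For a patient who came into the trial on extended half-life FVIII, the wording about a previous concentrate or a familiar pre-trial drug refers to exactly the class that 5.3.3 prohibits. A reader of 5.5 would take use of that product for a bleed on concizumab as allowed. A reader of 5.3.2 or 5.3.3 would take it as excluded.

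The conflict can arise in practice because bleeds are largely handled at home. Section 5.3.2 lets the patient treat himself and call the site afterwards, and Table 8-3 allows mild or moderate bleeds to be treated before contact with the investigator. An infusion can therefore be given in good faith under one section before anyone at the site can apply the other. Afterwards it could be recorded as permitted treatment or as a protocol deviation, depending on which section was read.

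**Working it through.** The protocol gives no figure on this point, so the check sets the passages side by side for one patient: an enrolled user of extended half-life FVIII.

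**Step 1. Can such a patient be in the trial?** Yes. Prophylaxis patients are eligible (5.1), no inclusion or exclusion criterion restricts the FVIII product (6.2, 6.3), and 8.1.7 makes provision for these users. That provision concerns treatment "For prophylactic treatment (prior to Screening) with extended half-life FVIII products" and its timing. It shows that the patients were foreseen; it does not itself authorise use of the product after screening.

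**Step 2. What does each passage say about his own product?**

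| Period and use | Text that permits it | Text that excludes it | Depends on the scope of 5.3.3? |
|---|---|---|---|
| Breakthrough bleed on concizumab | 5.5; Table 5-1 note | 5.3.2, first paragraph; 5.3.3 | No |
| Prophylaxis in screening | 8.1.7; Table 5-1 note | 5.3.3 as written | Yes |
| Prophylaxis in follow-up | 5.3.2, second paragraph (at the investigator's discretion); Table 5-1 note | 5.3.3 as written | Yes |

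**Step 3. Which conflicts survive a narrow reading of 5.3.3?** Suppose it covers only the concizumab treatment period. Rows two and three then contain no conflict, because nothing else excludes the product for prophylaxis in those periods. Row one is unchanged: a bleed on treatment falls inside that period on any reading, and the first paragraph of 5.3.2 excludes the product independently of 5.3.3.

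**Step 4. Does any passage settle row one?** In part. The Table 5-1 cell sends the reader to 5.3.2, which carries the non-modified limit. Section 5.5 has no such pointer and gives the permission outright. The treatment sections state no order of precedence among themselves.

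**Step 5. How many patients?** The protocol plans for 33 to start trial product and does not say how many will come from extended half-life FVIII. The number could be zero, and the text gives no basis for an estimate.

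**The case against.** The strongest case on the other side is that the operative sections agree and the rest is loose wording. Sections 5.3.2 and 5.3.3 stand next to each other and say the same about bleeds. Table 5-1 defers to 5.3.2. Section 5.5 is a rationale section, and its sentence mainly explains that the supplied product is not compulsory and that others are not reimbursed. Section 5.3.3 can be read as covering concizumab treatment only, since 5.4 deals separately with treatment afterwards.

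Much of this stands. It reduces the conflict in Table 5-1 and makes the screening and follow-up conflicts conditional. It does not remove the one in 5.5, which grants without qualification, for bleeds on treatment, what the two preceding sections withhold.

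A reader might also infer more than the text supports:

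- *That a site cannot comply with every passage.* It can. Table 5-1, 5.5 and 8.1.7 only permit, and turoctocog alfa is supplied in screening, treatment and follow-up.
- *That the prohibited product is prescribed in follow-up.* The wording there is directive but subject to the investigator's discretion. The next sentence names turoctocog alfa as the product supplied for that purpose, and 8.1.10.3 presents its use between visits 16 and 17 as optional.
- *That the prohibition exists because of thromboembolic risk in combination with concizumab.* Section 5.3.3 gives no reason.
- *That the primary endpoint is biased by longer cover after a rescue infusion.* The protocol states neither the half-lives concerned nor the number of users. Rescue dose is at the investigator's discretion up to the 50 IU/kg single-dose cap, and Table 8-4 guides repeat dosing over days, so cover already varies between patients.

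**Conclusion.** The contradiction is real and should be corrected, in a limited form. The firm part is the treatment of breakthrough bleeds during concizumab: 5.5, and less clearly the Table 5-1 note, permit a patient's own FVIII of any type, while 5.3.2 and 5.3.3 exclude extended half-life products. This rests only on the wording and on the eligibility of such users.

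The conditional part is prophylaxis in screening and follow-up. It conflicts with 5.3.3 as written, because no period is named, and falls away if the prohibition was meant for concizumab treatment alone.

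The size cannot be given in patients or in bleeding rate. The consequence is that a stated permission can lead to use of a product prohibited elsewhere in the same protocol, and that the same infusion can be classified in two ways. No effect on the trial's efficacy conclusion is shown.

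**What to change.** State in 5.3.3 which trial periods the prohibition of extended half-life FVIII covers: screening, concizumab treatment, follow-up, or a named subset. Then make Table 5-1, both paragraphs of 5.3.2, section 5.5 and section 8.1.7 agree with that statement, and check that 5.4 is consistent for patients who stop trial product early and still attend visit 17. Which rule applies in each period is the sponsor's clinical decision; the requirement here is that the passages be reconciled.

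The cost is amendment wording and retraining of sites and patients. No further patients or data collection are needed: section 8.3.1 already has FVIII and other product administrations recorded for each bleed.
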